#### **9.1.1. Adverse Events Leading to Discontinuation**

A summary of incidence rates (frequencies and percentages) of TEAEs leading to discontinuation of the study drug, by treatment group, SOC, and preferred term will be provided for the Safety Population. Additionally, this table will be repeated for TEAEs leading to study discontinuation.

#### **9.1.2. Deaths and Serious Adverse Events**

Any deaths that occur during the study will be flagged in the AE listing.

### **9.2. Local Tolerability Assessments**

The investigator's assessment of the application site reaction will be summarized by study visit using both categorical methods (number and percentage of subject with each score) as well as continuous methods (e.g., mean, median, etc.). Categorical summaries will be provided for dermal response as well as other effects.

Investigator tolerability assessment is performed before the subject is dosed on Baseline Day 0. Subject tolerability assessment is performed 10-15 minutes after the application of IP. Subjects not meeting this condition are excluded from table summaries for tolerability assessments.

The subject's assessment of the application site reaction will be summarized similarly.

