### 4.8.2. Treatment Administration

Initial treatment with the IP will occur on Day 0. At the randomization visit (Baseline), the study staff will demonstrate to the subject how to apply ARQ-154 foam 0.3% or vehicle foam using the first canister from the kit that is assigned to the subject at randomization. Study site staff will be trained to ensure a proper amount is dispensed from the foam can and applied to seborrheic dermatitis lesion(s) as a thin film and rubbed in thoroughly but gently, until the ‘white’ has disappeared. **For scalp lesions, special attention should be given to ensuring adequate investigational product is applied to scalp skin and not rubbed off on hair.** The subject will then practice dispensing a similar amount of investigational product and applying to seborrheic dermatitis lesion(s). The study staff will confirm that the subject’s application technique is correct.

Subjects will be instructed to apply IP QD in the evening (except at Baseline and Week 2, in which case IP will be applied at the study site) to areas of seborrheic dermatitis lesions identified by the Investigator at Baseline using a Body and Scalp Diagram (see [Appendix 1](#)). IP will be applied at least 20 minutes before going to bed.

For Scalp Lesions: IP will be applied when the skin and hair on the scalp is dry. Subjects should dispense IP on their fingers, then part hair where there are lesions and rub IP into scalp skin. As the IP is applied, the subject should move any hair away to ensure that sufficient foam is applied directly to the affected skin on the scalp. Subjects should not use other hair products for at least an hour before or after application.

For Non-scalp Lesions: IP should be applied to affected areas as a thin layer and rubbed in thoroughly but gently until the foam has disappeared.

Subjects should not wash areas (or otherwise expose to water, e.g., swimming) where ARQ-154 foam or vehicle has been applied until at least 4 hours after IP application and preferably not until the following morning.

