#### Other Effects

- A = slight glazed appearance
- B = marked glazing
- C = glazing with peeling and cracking
- D = glazing with fissures
- E = film of dried serous exudates
- F = small petechial erosions and/or scabs
- G = no other effects

The Subject Local Tolerability Assessment will be performed according to the Schedule of Visits and Assessments ([Section 1.3](#)).

This assessment will be administered by the site 10 to 15 minutes after IP application in the clinic at Baseline and recall assessments at Weeks 4 and 8.

Grade	Sensation Following Investigational Product Application
0 (none)	No sensation
1 (mild)	Slight warm, tingling sensation; not really bothersome
2 (moderate)	Definite warm, tingling sensation that is somewhat bothersome
3 (severe)	Hot, tingling/stinging sensation that has caused definite discomfort

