#### **6.2.4. Local Tolerance Assessments**

For both the Investigator's and Subject's assessment of the numeric application site reaction, scores will be summarized individually by using number and percentage of subjects by visit, as well as mean/median scores.

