***Footnotes from table above:***

- a Subjects that terminate early should return to the study site for the Week 8 assessments.
- b Limited physical examination: skin (including assessment of Fitzpatrick Skin Type at Screening only), lungs, and heart only.
- c To be collected at Screening, Baseline/Day 0, Week 4/Day 28, and Week 8/Day 56. For subjects <18 years of age, if the Baseline/Day 0 visit occurs within 3 weeks of Screening, the Screening lab results may be utilized.
- d Height will be collected at Baseline and Week 8. Weight will be collected at all study visits. Subject to void prior to weight.
- e IGA will be a 5-point scale ranging from clear (0) to severe (4). **IGA should be completed prior to other physician assessments and by the same Evaluator at each study visit.** Overall Assessment of Erythema (0-3 scale) and Overall Assessment of Scaling (0-3 scale) will be completed.
- f Total BSA affected by seborrheic dermatitis will be determined by the subject's hand method, where the subject's hand (including fingers) surface area is assumed to equal 1% of body surface area.
- g The DLQI will be completed by subjects  $\geq$ 17 years of age. The CDLQI will be completed for subjects 9 to 16 years old, inclusive.
- h WI-NRS will be completed by subjects daily at home starting 7 days prior to the Baseline/Day 0 visit to Day 56 (Week 8) visit. Daily WI-NRS will be completed in the evening prior to IP application (except at Baseline and Week 2 when IP is applied at the clinic).
- i Local tolerability assessments to be recorded prior to IP application for the Investigator assessment of skin irritation (Berger and Bowman skin irritation score) and 10-15 minutes post IP application for the subject's '0- 3' burning/stinging assessment. Note for investigator tolerability assessments: reactions at the site of IP application, which may occur post-Baseline, should be differentiated from the preexisting inflammation associated with the subject's seborrheic dermatitis. At Week 4 and Week 8, subjects will provide a recall assessment of burning/stinging experienced post IP application on the day prior to the clinic visit.
- j An assessment for hypopigmentation and hyperpigmentation will be performed by the Investigator at all clinic visits.

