## 6. GENERAL ISSUES FOR STATISTICAL ANALYSIS

### 6.1. Statistical Definitions and Algorithms

#### 6.1.1. Baseline

Baseline is defined as Study Day 1. In general, the last observation recorded before the first dose of study drug will be used as the baseline for all calculations of change from baseline. For assessments where time was recorded, the last observation recorded before the first application of study drug will be used as the baseline observation for all calculations of change from baseline. If the last non-missing assessment is performed on the same date as the first study treatment administration and time is not available, it is assumed that the assessment took place prior to IP application, per study site training, and the assessment will be considered as baseline, except for adverse events (AEs) and medications starting on the first study treatment dose

administration date which will be considered post baseline.

Average weekly baseline WI-NRS is defined as the average of all non-missing scores reported during the last 7 days prior to treatment if at least 4 of 7 evaluable daily WI-NRS questionnaires are available. Daily baseline WI-NRS is defined as the last non-missing assessment prior to the first study treatment.

For subject tolerability assessments, baseline is derived as the last non-missing measurement taken on the day of first application of study drug.

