### **9. SAFETY AND TOLERABILITY ANALYSIS**

All safety analyses will be performed on the Safety population. No inferential statistical tests will be performed.

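### SAP 9.2 drops whole subjects from the tolerability tables on a timing condition that only the Day 0 subject score can meet, without limiting the exclusion to that visit or that score

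*SAP*

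**What the plan says.** SAP 9.2 first describes how the investigator's application-site assessment is summarized by visit. It then notes that the investigator assesses before dosing on Day 0, and continues: "Subject tolerability assessment is performed 10-15 minutes after the application of IP". The next sentence is the exclusion: "Subjects not meeting this condition are excluded from table summaries for tolerability assessments". The section ends by saying the subject's assessment is handled in the same way as the investigator's.

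The collection rules are elsewhere. Protocol 5.1.11 has the site administer the subject score "10 to 15 minutes after IP application in the clinic at Baseline and recall assessments at Weeks 4 and 8". Footnote i of the SAP's own schedule (SAP Table 1) says that at Weeks 4 and 8 "subjects will provide a recall assessment of burning/stinging experienced post IP application on the day prior to the clinic visit". Protocol 4.8.2 has subjects dose in the evening, "except at Baseline and Week 2, in which case IP will be applied at the study site".

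On analysis, Protocol 6.2.4 plans that for both the investigator and the subject assessment "scores will be summarized individually by using number and percentage of subjects by visit". SAP Section 9 states: "All safety analyses will be performed on the Safety population". SAP 6.1.1 says that for the subject score "baseline is derived as the last non-missing measurement taken on the day of first application of study drug", with no timing condition. SAP 14.1 plans five tolerability tables by visit: 14.3.2.1 to 14.3.2.3 for the investigator scores, and 14.3.2.4 and 14.3.2.5 for the subject scores.

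**The concern.** An exclusion rule for a safety table has to say which record it removes. This one leaves two things open: the visits at which the condition is checked, and whether failing it removes one score or the whole subject. It also reaches tolerability summaries in general, so by its wording it is not confined to the subject-rated tables.

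Local tolerability is a listed safety endpoint (SAP 2.2.2) for a foam applied to the face, scalp and intertriginous areas. Tables 14.3.2.4 and 14.3.2.5 are the planned summaries of subject-rated burning and stinging. If a subject drops out of them, or out of the investigator tables, because the Day 0 question was asked a few minutes late, scores with nothing wrong with them are lost. The denominators at Weeks 4 and 8 would then also depend on how the text was programmed.

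**Working it through.** The plan states no figure to reproduce here. The check sets the condition against the schedule and then counts what each reading would remove.

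**Step 1. Where can the condition be met?** Sources: the visit schedules (Protocol 1.3, SAP Table 1), Protocol 4.8.2 and 5.1.11, and SAP Table 1 footnote i.

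| Visit | Dosing on site | Tolerability scheduled | Subject score obtained by | Can meet 10–15 min |
|---|---|---|---|---|
| Baseline Day 0 | yes | yes | timed rating in clinic | yes |
| Week 2 | yes | no | none | not applicable |
| Week 4 | no | yes | recall of previous day | no |
| Week 8 | no | yes | recall of previous day | no |

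So 1 of 3 scheduled subject scores can meet the condition, and 0 of 2 after baseline. Subject tolerability may also be collected remotely (Protocol Appendix 11, SAP 6.2), which fits a recall question and not a timed one.

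**Step 2. Inputs for scale.** About 450 subjects are planned, 300 active and 150 vehicle (SAP 3.2). Full attendance is assumed. Planned subject scores: 450 × 3 = 1,350. Adding one investigator assessment at each of the same three visits: 450 × 6 = 2,700. The share *m* of Day 0 scores outside the window is not given, so 2% to 10% is used as an illustrative assumption.

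**Step 3. Readings.**

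- *Condition checked at every visit, score by score.* Failing scores: 450 × 2 = 900 (600 active, 300 vehicle). 900 / 1,350 = 66.7%. The Week 4 and Week 8 subject rows are empty.
- *Day 0 only, removing just the mistimed score.* 450 × *m* = 9 to 45 scores. 9 / 1,350 = 0.7%; 45 / 1,350 = 3.3%. Nothing after baseline is lost.
- *Day 0 only, removing the subject from all tolerability tables.* 9 to 45 subjects, with 6 assessments each: 54 to 270 of 2,700, or 2% to 10%. For each such subject only 1 of the 6 is mistimed. The other 5 (two recalls, three investigator assessments) were collected as planned: 9 × 5 = 45 up to 45 × 5 = 225. Of these, 4 per subject are post-baseline: 36 to 180.

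**Step 4. Which reading does the text support?** The sentence before the timing condition names Day 0, and the tables are planned by visit, so a check on Day 0 only is the likely intent. The unit of exclusion is nevertheless the subject, and its scope is tolerability summaries as a whole. The literal consequence on the likely reading is therefore the third bullet. That sits badly with a by-visit summary of both assessments (Protocol 6.2.4) in the full Safety population (SAP Section 9).

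**The case against.** The strongest reply is that SAP 9.2, read as a whole, plainly concerns Baseline. The investigator sentence and the subject sentence form a pair describing the in-clinic dosing visit. Footnote i has the same shape: it gives the 10 to 15 minute timing without a visit and then sets Weeks 4 and 8 apart as recall. The by-visit tables would make no sense if two of three visits were empty. This stands. A reader might infer from the literal wording that the plan discards every post-baseline burning/stinging score, 900 of 1,350. The documents do not support that as the intended analysis, and nothing in them shows that any score was dropped.

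Further replies also carry weight. The by-visit layout is compatible with removing a subject only from the affected visit's row. The table shells, which might settle the matter, are in a separate document (SAP 15.1). Protocol 6.1 describes its methods as a summary of what the SAP will detail, so a handling rule first appearing in the SAP is not clearly an undeclared change for Section 12. The SAP 6.1.1 baseline definition selects a record and can coexist with a table filter. The missing tolerability listing in SAP 14.3 is part of a generally short listing plan and is not caused by this rule.

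What these replies do not remove is the wording. The text says subjects, does not confine the loss to the Day 0 row, and does not confine it to the subject-rated tables. Likely intent settles the visit; it does not settle the unit or the scope.

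**Conclusion.** The point holds as a faulty stated rule in a descriptive safety analysis. The condition can be met only at Day 0 and was probably meant only for Day 0. Even so, the rule as worded can remove a mistimed subject's valid Week 4 and Week 8 recalls and all of that subject's investigator scores.

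The size is unknown. On the assumed 2% to 10% mistiming it would be 9 to 45 subjects and 36 to 180 post-baseline assessments. With no mistiming it would be zero. These counts also assume 450 subjects and full attendance. The 67% loss belongs to a reading that the SAP's own context argues against and should not be quoted as the expected effect.

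No inferential test is planned on safety data (SAP Section 9), so efficacy, alpha and power are unaffected. Correction is still worthwhile because it costs very little and the data are already collected.

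**What to change.** Reword SAP 9.2 to say that:

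- the 10 to 15 minute condition applies only to the Baseline Day 0 subject score;
- Day 0 scores outside the window are flagged and kept or, if an exclusion is preferred, only that score is left out and the number left out is shown per arm;
- all Week 4 and Week 8 recall scores, and all investigator scores, are summarized by visit in the Safety population, with the later subject rows labelled as recall.

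The database was locked on 17 May 2022 and unblinded on 19 May 2022 (SAP Section 1), so the CSR should state which rule was programmed. Tables 14.3.2.1 to 14.3.2.5 need a rerun only if scores other than mistimed Day 0 subject scores were dropped. A tolerability listing in SAP 14.3 and an entry in Section 12 would help but are optional.

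The cost is one SAP paragraph, a sentence in the CSR and, at most, a rerun of five descriptive tables. No new data, visit or protocol amendment is needed.

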### **9.3. Clinical Laboratory Evaluations**

Laboratory test results will be summarized descriptively by treatment and study visit as both observed values and change and percent change from baseline values for continuous hematology, chemistry, and urinalysis results. Categorical urinalysis results will be summarized using frequencies by study visit and treatment.

The number of subjects with clinical laboratory values below, within, or above the normal range by study visit and in relation to baseline will be tabulated for each clinical laboratory analyte by treatment group (shift table).

Abnormal laboratory values will be listed.

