### 5.1.6. Laboratory Tests

All tests listed in Table 2 will be performed according to the Schedule of Visits and Assessments ([Section 1.3](#)) unless otherwise noted. For subjects <18 years old, Screening safety lab results collected within 3 weeks of the Baseline visit may be utilized as the Baseline safety lab assessment. No food restrictions are required for the collection of specimens. In addition, laboratory safety tests may be performed at unscheduled time points, if deemed necessary by the Investigator. Laboratory samples will be sent to the central lab. Refer to the most current Central Laboratory Manual for collection, processing, shipping, and report receipt instructions.

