### **6.2.2. Clinical Laboratory Results**

Shifts in clinical laboratory parameters from Baseline to worst post-Baseline grade will be provided.

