### 6.1.5. Analysis Visit Windows

Visits will be analyzed as scheduled. Unscheduled, early termination visits, and/or repeated measurements will only be included if a scheduled measurement is not available, and the early termination or unscheduled/repeated measurement falls within the analysis visit windows as described in [Table 2](#). Unscheduled/repeated measurements will be listed.

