# **10. CHANGES FROM PLANNED ANALYSIS**

## **10.1. Version 2.0**

Version 2.0 of the SAP is based on the final signed version of Amendment 2 for the ARQ-154-304 protocol. At the time of signing this SAP version 2.0, the protocol is in the process of being published and is planned to undergo IRB review and approval after database lock.

The intent of this SAP is to document, prior to study database lock and unblinding, the changes specified in protocol amendment 2 regarding the testing strategy used for the secondary endpoints and also other minor updates to analyses not detailed in the protocol. Any changes to the final protocol or additional analyses created after database lock and unblinding will be clearly labeled as such in the CSR.

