## **10.2. Version 3.0**

Section 1 Overview provides a description of the rationale for SAP Version 3. The purpose of the SAP is to document the change to the primary estimand and related multiple imputation strategies. The revised estimand will be the focus of the Clinical Study Report and NDA. Key results based on the original estimand defined in SAP versions 1 and 2 will be provided as supplemental information for the primary and secondary endpoints covered by the multiple

testing strategy.

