## **12. CHANGES TO ANALYSIS PLANNED IN THE PROTOCOL**

### **12.1. Definition of PK Population**

In this SAP, PK population is defined as subjects who received at least one confirmed dose of investigational product (IP) and provided at least one PK sample. This population will be used for summary of PK concentration results. The definition is different from that in protocol where PK population is defined as subjects receiving active drug with sufficient plasma concentrations of roflumilast to define a profile, as determined by the pharmacokineticist, which will be used for analysis of PK parameters.

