14.3.3.1	Safety	Summary of Clinical Chemistry Laboratory Results (Standard Units) by Study Visit
14.3.3.2	Safety	Shift from Baseline in Clinical Chemistry Laboratory Results (Standard Units) by Study Visit
14.3.3.3	Safety	Summary of Hematology Laboratory Results (Standard Units) by Study Visit
14.3.3.4	Safety	Shift from Baseline in Hematology Laboratory Results (Standard Units) by Study Visit
14.3.3.5	Safety	Summary of Quantitative Urinalysis Laboratory Results (Standard Units) by Study Visit
14.3.3.6	Safety	Shift from Baseline in Quantitative Urinalysis Laboratory Results (Standard Units) by Study Visit
14.3.3.7	Safety	Summary of Qualitative Urinalysis Laboratory Results (Standard Units) by Study Visit
14.3.4.1	Safety	Summary of Vital Signs by Study Visit
14.3.4.2	Safety	Change in Weight from Baseline by Study Visit
14.3.4.3	Safety	Shift from Baseline in BMI by Study Visit
14.3.4.4	Safety	Change in Weight from Baseline by Study Visit – by Weight Loss Intentional/Non-Intentional
14.3.4.5	Safety	Shift from Baseline in BMI by Study Visit - by Weight Loss Intentional/Non-Intentional
14.3.5	Safety	Shift from Baseline in Patient Health Questionnaire (PHQ-8)/Modified PHQ-Adolescents by Study Visit
14.3.6	Safety	Summary of CDI-2 by Study Visit
14.3.7	Safety	Summary of Columbia-Suicide Severity Rating Scale (C-SSRS) Suicidal Ideation and Suicidal Behavior by Study Visit
14.3.8	Safety	Summary of Physical Examination by Study Visit
14.3.9	Safety	Summary of Concomitant Medications by Anatomic Therapeutic Chemical (ATC) Class Level 4 and Preferred Term
14.3.10	Safety	Summary of Pigmentation Assessment by Race
14.3.10.1	Safety	Shift from Baseline in Hypopigmentation by Study Visit
14.3.10.2	Safety	Shift from Baseline in Hyperpigmentation by Study Visit
14.4	Pharmacokinetic Data	
14.4.1	PK	Summary of Pharmacokinetic Concentration Results by Study Visit

\*Analyses of Scalpdex will be limited to subjects in the ITT population who have Seborrheic Dermatitis involvement on the scalp

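### The SAP plans by-visit normal-range laboratory shifts in place of the protocol's Baseline-to-worst-grade shift, and does not declare the change

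*SAP*

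**What the plan says.** Protocol 6.2.2 consists of a single sentence: "Shifts in clinical laboratory parameters from Baseline to worst post-Baseline grade will be provided". It names no grading scale. Appendix 10 of the protocol gives laboratory Grades 1 to 3, and section 5.9 refers to that appendix when it makes a confirmed treatment-emergent Grade 3 laboratory abnormality a reason to discontinue treatment.

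SAP 9.3 plans descriptive summaries by visit, frequencies for categorical urinalysis, a listing of abnormal values, and a shift table of "clinical laboratory values below, within, or above the normal range by study visit and in relation to baseline". The table list in SAP 14.1 follows the same pattern. Table 14.3.3.2, for instance, is titled "Shift from Baseline in Clinical Chemistry Laboratory Results (Standard Units) by Study Visit".

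On off-schedule data, SAP 6.1.5 states: "Unscheduled, early termination visits, and/or repeated measurements will only be included if a scheduled measurement is not available". Protocol 5.1.6 expects such data to exist, since "laboratory safety tests may be performed at unscheduled time points, if deemed necessary by the Investigator".

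SAP section 12, which is meant to record departures from the protocol, has one entry: "Definition of PK Population". For SAP Version 3.0, section 10.2 states: "The purpose of the SAP is to document the change to the primary estimand and related multiple imputation strategies".

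**The concern.** A category of below, within or above normal is not a grade, and a shift at each visit is not a shift to the worst value. As planned, no table shows how many subjects in each arm reached Grade 1, 2 or 3 at any time after Baseline.

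That comparison matters here. Safety is part of the primary objective, the sample size was set partly to supply a safety database (Protocol 6.1.1), and a laboratory grade is one of the treatment stopping criteria. A reader who relies on the protocol would expect the graded table in the study report, and nothing in the SAP says that it was dropped or why.

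**Working it through.** No sample size, alpha or power figure bears on this point, so the check is a comparison of texts plus some counting.

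**1. Commitment against plan.**

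| | Protocol 6.2.2 | SAP 9.3 and 14.1 |
|---|---|---|
| Scale | Grade | Below, within or above normal |
| Time | Worst post-Baseline | Each study visit |

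Tables 14.3.3.1 to 14.3.3.7 make seven laboratory tables. All seven titles are by study visit, three are shift tables (14.3.3.2, 14.3.3.4, 14.3.3.6), and none is graded or worst post-Baseline. No SAP section assigns a grade to a laboratory value or derives a worst one.

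**2. Is the change declared?** Section 12 covers only the PK population. Section 10.2 covers the estimand and imputation. Section 10.1 covers the secondary testing strategy and minor updates to analyses that the protocol does not detail; Protocol 6.2.2 does detail this one, so that wording does not reach it.

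**3. Grade resolution, using ALT.** Appendix 10 sets Grade 1 at above ULN to 3x, Grade 2 at above 3x to 5x, and Grade 3 at above 5x ULN. Exclusion 11 excludes ALT only above 2x ULN, so a subject can enter at 1.5x ULN, which is Grade 1. A rise to 6x ULN is Grade 3. The SAP table places this subject above normal at Baseline and above normal afterwards, so no shift is shown. For a subject with normal ALT at Baseline, later Grades 1, 2 and 3 all fall in the same within-to-above cell.

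**4. Worst value per subject.** The visit schedule places post-Baseline laboratory draws at Weeks 4 and 8 only. For scheduled data the worst value is therefore the worse of two, and both are tabulated. The by-visit tables still do not count subjects: if *a* subjects in an arm are above normal at Week 4 and *b* at Week 8, the number ever above normal can be anything from max(*a*, *b*) to *a* + *b*.

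**5. Off-schedule values.** The windows in SAP 6.1.5 are Days 2–22 (Week 2), 23–42 (Week 4), and 43 onward (Week 8).

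- Days 2–22: no laboratory draw is scheduled at Week 2, so on a plain reading an unscheduled draw can be tabulated as Week 2.
- Day 23 onward: an unscheduled, repeat or early-termination value is left out if a scheduled value exists in the same window.
- In the usual repeat-test case (Protocol 5.6) the scheduled abnormal value stays in the table. The remaining gap is a worse value first found off-schedule, or a repeat worse than the scheduled value.

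**6. Can the protocol's table be built?** Protocol Table 2 lines that have limits in Appendix 10:

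- Chemistry: 10 of 11 (none for chloride).
- Hematology: 3 of 5 (none for hematocrit or for red cell count with indices; the leukocyte differential is covered in part).
- Urinalysis: 3 of 10 (protein, glucose, and blood by microscopy, which is done only after a positive result).

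The total is 10 + 3 + 3 = 16 of 11 + 5 + 10 = 26, leaving 26 − 16 = 10 without a grade. This counts creatinine as graded. Appendix 10 marks it N, defined there as not graded, yet gives limits. If it is excluded, the split is 15 graded and 11 ungraded.

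**The case against.** The strongest reply is that little is lost. With two scheduled post-Baseline draws, all scheduled values are already in the by-visit tables. SAP 4.1 includes the minimum and maximum in continuous summaries, so an extreme scheduled value is visible by arm and visit. Abnormal values are listed (16.3.2.1 to 16.3.2.3). A confirmed Grade 3 result leads to discontinuation under Protocol 5.9. Protocol 5.7.1 counts as an AE a laboratory finding that requires an adjustment of therapy, so such a case would arguably reach the AE and discontinuation tables. Safety analyses are descriptive, and the table shells are a separate document not available here.

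Much of this stands, and it limits the size of the point. It does not supply the promised comparison. A maximum shows one value, not how many subjects reached a grade or where they started. The AE route is partial: Protocol 5.7.1 in general leaves out findings judged not clinically significant and, where applicable, records the sequelae instead of the laboratory abnormality. The shells could differ, but the SAP's own text and table list contain no such table.

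It may also be said that Protocol 6.1 defers disclosure to the study report. That sentence concerns changes to methods in the final SAP, not a SAP that already differs from the protocol.

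A reader might infer three stronger things that the documents do not support:

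- That laboratory data or signals are lost. The values are still listed, and other tables catch some cases.
- That off-schedule results generally vanish from the tables. The exclusion applies only where a scheduled value shares the window, in practice from Day 23.
- That the graded table was removed after the results were seen. The SAP version history names no laboratory change in Version 2.0 or 3.0. Version 1.0 is not available, so the origin of the difference is unknown.

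**Conclusion.** The point holds as an undeclared departure of the SAP from the protocol in a descriptive safety analysis. What is missing is the grade and the per-subject worst value by arm, together with a narrow set of off-schedule values from Day 23. Efficacy conclusions, alpha and power are unaffected. The number of subjects or results affected cannot be derived from the documents.

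The conclusion rests on two assumptions: that the SAP table titles reflect the tables to be produced, and that Appendix 10 is the scale that Protocol 6.2.2 intends. The second is the natural reading, because section 5.9 cites Appendix 10 for laboratory grade, but 6.2.2 does not say so. The departure should be corrected, because the protocol states the analysis explicitly and restoring it is cheap.

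**What to change.** Add to SAP 9.3 and 14.1 a shift table by arm from Baseline to worst post-Baseline grade, and specify:

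- All scheduled and unscheduled post-Baseline results are used; the rule in SAP 6.1.5 that prefers scheduled values does not apply to this table.
- The grading scale by name (Appendix 10, if that is what was meant).
- For Table 2 lines without a grade, such as chloride and hematocrit, the worst normal-range category, or the worst category for dipstick tests.
- How creatinine is handled, given its N mark alongside stated limits.

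The database is locked and unblinded, so the study report should label the table as the Protocol 6.2.2 analysis, added to the SAP after unblinding. SAP 10.1 already calls for this: "Any changes to the final protocol or additional analyses created after database lock and unblinding will be clearly labeled as such in the CSR". If the table is not restored, declare and justify the omission in SAP section 12.

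The cost is a few descriptive tables from existing data and short wording changes. No new data are needed.
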